3.4.2 Safety Endpoints

For all Parts of the study, safety and tolerability assessments will include adverse events, laboratory abnormalities, ECGs, and vital sign measurements including supine blood pressure. Exploratory PK and PD assessments will also be made in all parts of the study as indicated in the schedule of assessments.

3.5 Minimization of Bias

Bias will be minimized through the use of randomization and blinding.

3.5.1 Blinding

In Part A, study subjects will be blinded to dose levels and escalation. Pre-defined stopping rules will be used to guide procedures. For Part B, which has been discontinued, refer to previous versions of this protocol. Part C will be an open-label extension study and therefore blinding considerations are not applicable.

3.5.2 Treatment Assignment

Subjects in Part A will begin by receiving placebo in a single-blind manner (ie, subject remains blinded). This will be followed by daily dose escalations, beginning with [REDACTED] of TD-9855 on Day 2. On each subsequent day, subjects will receive a single escalating dose of TD-9855 [REDACTED] until Day 5 or until reaching the preset stopping criteria

(Section 5.2). However, based on the daily evaluation of tolerability, the Investigator (in collaboration with the Sponsor), may decide to not escalate the dose, but rather re-administer the previous dose from the prior day. Once the decision has been made to not escalate the dose, the subject should remain at the current dose through Day 5 of dosing.

The dose level administered on Day 1 in Part C will be equal to 50% of the highest tolerated dose level (rounded up to the nearest 1 mg) administered during Part A for that subject (or a lower dose at the discretion of the principal investigator to manage individual subject safety). Subjects will be discharged from the research clinic on Day 2 and continue at the same dose level as Day 1 of Part C. At the subsequent scheduled visits until Day 29, the Investigator has the option to double the subject's dose level at their discretion, if in their opinion the subject will benefit from, and can tolerate, a higher dose level. After Day 29, dose increases will need to be discussed with the Sponsor. It is recommended that the subject receives at least 7 daily doses of TD-9855 at any single dose level before escalation to a higher dose to allow TD-9855 exposure to reach steady state at the lower dose. Due to the half-life of TD-9855 multiple dose increases within a 7 day period might lead to greater than 2-fold increase in TD-9855 exposure and are not recommended. The maximum dose administered to any subject is [REDACTED]. The schedule for dose increases is shown in Table 3.

Table 3: Weekly Dose Escalation Plan for Subject in Part C

Part A Maximum Dose	Part C Day 1 dose	Part C Day 8 dose	Part C Day 15 dose	Part C Day 22 dose	Part C Day 29 dose
[REDACTED]	[REDACTED]	[REDACTED]	[REDACTED]	[REDACTED]	[REDACTED]
[REDACTED]	[REDACTED]	[REDACTED]	[REDACTED]	[REDACTED]	[REDACTED]
[REDACTED]	[REDACTED]	[REDACTED]	[REDACTED]	[REDACTED]	[REDACTED]

In the case where a subject develops the presence or worsening of supine hypertension (as determined by the Investigator with agreement from the Sponsor) or other adverse events suggesting intolerance, the dose can be withheld for 3 days and resumed at a dose level 50% (rounded up to the nearest 1 mg) of the prior dose level. If supine hypertension or other adverse events persists after the dose has been reduced, dosing in that subject should be discontinued and appropriate alternative therapy and care provided to the subject as determined by the principal investigator.

4 STUDY POPULATION

Subjects who meet all of the inclusion and none of the exclusion criteria will be eligible for enrollment into this study.

4.1 Inclusion Criteria

1. Male or female at least 40 years of age.
2. Subject is able to communicate well with the Investigator and understands the expectations of the study.
3. Subject is willing and able to comply with the study procedures, requirements and restrictions, and to understand and signed the informed consent form.
4. Subject has been diagnosed with symptomatic orthostatic hypotension due to Parkinson's disease, multiple system atrophy, or pure autonomic failure (ie, neurogenic orthostatic hypotension).
5. Subjects must meet the diagnostic criteria of neurogenic orthostatic hypotension, as demonstrated by a ≥ 30 mm Hg drop in SBP within 5 minutes of standing. If additional Autonomic Function Testing is required to confirm the diagnosis of autonomic dysfunction, sinus arrhythmia and Valsalva maneuver may be conducted, as appropriate.
6. Impaired autonomic reflexes, as determined by absence of BP overshoot during phase IV of the Valsalva maneuver, in subjects where Valsalva is performed, as appropriate.
7. Experiencing dizziness, light-headedness, or fainting when standing.
8. Absence of other identifiable causes of autonomic neuropathy.
9. Female subjects must be non-pregnant and non-lactating. If a female subject is of childbearing potential, must have a documented negative pregnancy test at screening.
NOTE: All females are considered to be of childbearing potential unless they are postmenopausal (amenorrheic for at least 2 years) or documented to be surgically sterile (bilateral tubal ligation or total hysterectomy). A subject may be admitted to the study on the basis of a negative urine pregnancy test (local lab), pending the result of the serum pregnancy test.
10. If sexually active, must agree to use a highly effective method of birth control with partners of childbearing potential during the study and for 1 month after study drug

dosing.

NOTE: A highly effective method of birth control is defined as one that results in a low failure rate (ie, < 1% per year) when used consistently and correctly, such as implants, injectables, combined oral contraceptives, some intra-uterine devices (IUDs), sexual abstinence, or a vasectomized partner. Male subjects must agree to use medically acceptable birth control for at least 1 month following last dose of study medication. A vasectomy or a condom used with a spermicide is a medically acceptable birth control method for males.

Additional criteria for subjects participating in Part C only:

11. Demonstrated a pressor effect in Part A and completed dosing in Part A.
12. Willing to sign an IRB-approved informed consent form for Part C.
13. Able to comply with the visit requirements for Part C.

4.2 Exclusion Criteria

1. Systemic illnesses known to produce autonomic neuropathy, including but not limited to diabetes mellitus, amyloidosis, and autoimmune neuropathies.
2. Known intolerance to other NRIs or SNRIs.
3. Pre-existing sustained hypertension (BP \geq 150/100 mm Hg in the sitting position determined from three independent assessments, and not explained by the use of pressor agents).
4. Concomitant use of vasoconstricting agents for the purpose of increasing BP such as ephedrine, dihydroergotamine, or midodrine must stop taking these drugs at least 2 days or five half-lives (whichever is longer) prior to dosing on Day 1 of Part A and C, and throughout the duration of Part C. Subjects previously enrolled in Part A under previous versions of the protocol will continue taking fludrocortisone during the washout period and in Part C at the dose and regimen used in Part A. For new subjects enrolling in Part A under Amendment 3, fludrocortisone use in both Parts of the study and during the washout period will be limited to 0.1 mg QD.
5. Concomitant use of anti-hypertensive medication for the treatment of essential hypertension unrelated to autonomic dysfunction.
6. Have changed dose, frequency or type of prescribed medication, within two weeks of dosing on Day 1 with the following exceptions:

- Vasoconstricting agents such as ephedrine, dihydroergotamine, midodrine, or fludrocortisone
- Short courses (less than 2 weeks) of medications or treatments that do not interfere with, or exacerbate the subject's condition under study (eg, antibiotics)

7. Known or suspected alcohol or substance abuse within the past 12 months (DSM-IV definition of alcohol or substance abuse).
8. Clinically unstable coronary artery disease, or major cardiovascular or neurological event in the past 6 months.
9. Use of any monoamine oxidase inhibitor (MAO-I) within 14 days of dosing on Day 1.
10. History of untreated closed angle glaucoma, or treated closed angle glaucoma that, in the opinion of an ophthalmologist, might result in an increased risk to the subject.
11. Any significant uncontrolled cardiac arrhythmia.
12. Myocardial infarction in the past 6 months, or current unstable angina.
13. Congestive heart failure (NYHA Class 3 or 4).
14. Diabetes insipidus, insulin-dependent diabetes mellitus, or diabetic neuropathy.
15. History of cancer within the past 2 years other than a successfully treated, non-metastatic cutaneous squamous cell or basal cell carcinoma or cervical cancer in situ.
16. Gastrointestinal condition, which in the Investigator's judgment may affect the absorption of study drug (eg, ulcerative colitis, gastric bypass).
17. Any major surgical procedure within 30 days of dosing on Day 1.
18. Any other significant cardiovascular, pulmonary, renal, endocrine, hepatic, neurologic, psychiatric, immunologic, hematologic, gastrointestinal, or metabolic disease not currently controlled with medical treatment (eg, a stable medication dosing regimen).
19. Currently receiving any investigational drug or have received an investigational drug within 30 days of dosing on Day 1. An investigational drug is defined as a non-FDA approved drug.
20. Allergic to or unable to drink apple juice (Part A only).

21. Any condition or laboratory test result which, in the Investigator's judgment, might result in an increased risk to the subject, or would affect their participation in the study.
22. Additionally, the Investigator has the ability to exclude a subject if for any reason they feel the subject is not a good candidate for the study or will not be able to follow study procedures.

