Visit number	Admit		Treatment period									Follow-up		
	1		2	3	4	5	6	7	8	9	10	11 EOS		
Study week (beginning of week except Day 140)				1	2	3	4	5	9	13	17	20	23	25
Procedure (Study Day)	Admit Day -2	Day -1 ^b	Day 1 ^b	Day 2 ^b	Day 8	Day 15	Day 22	Day 29	Day 57	Day 85	Day 113	Day 140 ^m	Day 155	Day 169
Overnight Residency	X ^a	X ^a	X ^a											
Informed Consent	X													
Review Inclusion/Exclusion Criteria	X	X												
Medication and Medical History	X ^c													
Weight/BMI & Temperature	X	X	X	X		X		X		X		X	X	X
Orthostatic Standing Test including supine blood pressure ^d		X ^d	X ^d	X ^d		X ^d		X ^d		X ^d		X ^d	X ^d	X ^d
Supine blood pressure ^e	X ^e				X ^e		X ^e		X ^e		X ^e			
24 hour blood pressure monitoring ^f		X ^f				X ^f		X ^f		X ^f				X ^f
ECG (12-lead)		X												X
Physical Examination ^g		X ^g	X ^g	X ^g		X ^g		X ^g		X ^g		X ^g	X ^g	X ^g
Urine Pregnancy Test ^h	X ^h													
Safety labs: Hematology, Chemistry, and UA	X ^o													X
PK Sampling ⁱ			X ⁱ	X ⁱ		X ⁱ		X ⁱ		X ⁱ		X ⁱ		X ⁱ
DHPG Sampling ^j			X ^j	X ^j				X ^j						
NE Sampling ^k			X ^k					X ^k						
OHQ (OHSA and OHDAS) ^l		X ^l	X ^l	X ^l	X ^l	X ^l	X ^l	X ^l	X ^l	X ^l	X ^l	X ^l	X ^l	
Clinician's/Subject's Global Impression ^l		X ^l	X ^l	X ^l	X ^l	X ^l	X ^l	X ^l	X ^l	X ^l	X ^l	X ^l	X ^l	
Concomitant Medications	X	X	X	X	X	X	X	X	X	X	X	X	X	X
Adverse Events	X	X	X	X	X	X	X	X	X	X	X	X	X	X
Study Drug Administration ^m			X ^m	X ^m	X ^m	X ^m	X ^m	X ^m	X ^m	X ^m	X ^m	X ^m	X ^m	
Subject Satisfaction Survey ⁿ			X ⁿ			X ⁿ		X ⁿ				X ⁿ		
Telephone Assessments (highlighted in gray)					X		X		X		X			

SCHEDULE OF STUDY ASSESSMENTS (CONTINUED)

- a. Subjects will admit to the research unit on Day -2 and remain resident through the completion of study procedures on the morning of Day 2.
- b. The timing of Day -1 "postdose" assessments should be prospectively calculated, based on the target Day 1 dosing time (eg, orthostatic standing test and Clinical Impression and OHQ assessments). Study Day 1 is defined as the day of first study dosing with TD-9855 in Part C. On Day 2 subjects are discharged from the research facility after all study procedures are completed the morning of Day 2.
- c. History update, if any changes since participation in Part A (and B if appropriate) of the study.

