- k. Blood collection for NE analysis will be collected on Day 1 (within 30 minutes before dosing) and upon return to the clinic on Day 29. Please refer to the central laboratory manual.

SCHEDULE OF STUDY ASSESSMENTS (CONTINUED)

- I. Clinician's/Subject's Global Impression and OHQ (OHSA and OHDAS components) to be administered during clinic visits by a trained clinician and recorded on standardized paper forms (See [Appendix 4](#)). In addition while at home, the Clinician's/Subject's Global Impression and OHQ will be completed by telephone with the study coordinator. On all visit days the OHQ and Global Impression assessments should be completed at least 4 hours after dosing (but no more than 7 hours) and before lunch. For the Day 155 and 169 assessments, the timing of the "postdose" questionnaires should be calculated based on the Day 1 dosing time.
- m. On the study visit days marked above, subjects will receive a dose of study medication in the morning after supine blood pressures and the orthostatic standing test has been completed. On non-study visit days the subjects should take their dose of study medication in the morning at approximately the same time of day. On study days where the subject is traveling to the clinic, the subject should take their dose of study medication at home before traveling to the clinic. Subjects will return to the clinic on the day of their final dose. Day 140 is the day of the last dose received at the end of 5 months (20 weeks).
- n. Subjects will complete the Subject Satisfaction Survey on Days -1, 15, 29 and 140 (or at the time of early discontinuation) using the appropriate questionnaire listed in [Appendix 5](#).
- o. Safety labs should be collected Day -2 or on Day -1.

Sequence of study procedures during study visits (with *hypothetical* times for illustration):

- 7:00 am -Wake up
- 7:30 am - supine blood pressure after 5 and 10 minutes resting at 30 degrees elevation and orthostatic standing test (where applicable)
- 8:00 am - Dose with TD-9855 and eat breakfast

After a minimum of 4 hours but no more than 7 hours after dosing and before lunch:

- 12:00 pm - supine blood pressure after 5 and 10 minutes resting at 30 degrees elevation and orthostatic standing test (where applicable)
- 12:30 pm - Clinician/subject impression and OH Questionnaires (OHDAS and OHSA)
- 12:45 pm - lunch

TABLE OF CONTENTS

	PAGE
PROTOCOL SYNOPSIS	2
SCHEDULE OF STUDY ASSESSMENTS	12
LIST OF ABBREVIATIONS AND DEFINITION OF TERMS	20

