Appendix 2: Orthostatic Hypotension Questionnaire (OHQ) for Part C Only

AUTONOMIC DYSFUNCTION SCORES ORTHOSTATIC HYPOTENSION QUESTIONNAIRE (OHQ)													
Patient Instructions:													

We are interested in measuring the symptoms that occur because of your problem with low blood pressure (orthostatic hypotension) and the degree that those symptoms may interfere with your daily activity. It is important that we measure the symptoms that are due ONLY to your low blood pressure, and not something else (like diabetes or Parkinson's disease). Many people know which of their symptoms are due to low blood pressure. Some people who have recently developed problems with low blood pressure may not easily distinguish symptoms of low blood pressure from symptoms caused by other conditions. In general, symptoms of your low blood pressure problem will appear either upon standing or after you have been standing for some time, and will usually improve if you sit down or lie down. Some patients even have symptoms when they are sitting which might improve after laying down. Some people have symptoms that improve only after sitting or lying down for quite some time.
 
Please answer the questions on the following pages keeping in mind that we want to know only about those symptoms that are from your problem with low blood pressure.
													
OH SYMPTOM ASSESSMENT (OHSA)													

Please tick the box on the scale that best rates how severe your symptoms from low blood pressure have been on the average over the past week. Please respond to every symptom. If you do not experience the symptom, tick zero (0). PLEASE RATE THE SYMPTOMS THAT ARE DUE ONLY TO YOUR LOW BLOOD PRESSURE PROBLEM.
													
1.	Dizziness, lightheadedness, feeling faint, or feeling like you might black out												
	None	 0	 1	 2	 3	 4	 5	 6	 7	 8	 9	 10	Worst possible
2.	Problems with vision (blurring, seeing spots, tunnel vision, etc.)												

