Appendix 4: Physician/Subject Global Impression for Part C Only

CLINICAL GLOBAL IMPRESSIONS – CLINICIAN (Part C only)

Clinical Global Impressions – Clinician

1) Severity of Illness

Considering your total clinical experience with the particular population, how severe is the patient's orthostatic hypotension (OH) at this time?

- 0 – Not assessed
- 1 – Normal, no OH
- 2 – Borderline OH
- 3 – Mild OH
- 4 – Moderate OH
- 5 – Marked OH
- 6 – Severe OH
- 7 – Among those patients most extremely ill with OH

2) Global Improvement – Rate total improvement regardless as to whether or not you believe it is due entirely to drug treatment.

Compared to the patient's condition at Day -1 (Admission) for Part C, how much has his/her orthostatic hypotension changed?

- 0 – Not assessed
- 1 – Very much improved
- 2 – Much improved
- 3 – Slightly improved
- 4 – No change
- 5 – Slightly worse
- 6 – Much worse
- 7 – Very much worse

Date completed: _____ time: _____ Initials: _____

CLINICAL GLOBAL IMPRESSIONS – PATIENT (Part C only)

Clinical Global Impressions – Patient

1) Severity of Illness

How severe is your orthostatic hypotension (OH) at this time?

- 0 – Not assessed
- 1 – Normal, no OH
- 2 – Borderline OH
- 3 – Mild OH
- 4 – Moderate OH
- 5 – Marked OH
- 6 – Severe OH
- 7 – Most extremely ill with OH

2) Global Improvement – Rate total improvement regardless as to whether or not you believe it is due entirely to drug treatment.

Compared to your condition at your Day -1 (Admission) visit when you rated the severity of your orthostatic hypotension after being off medication, how much has your condition changed?

- 0 – Not assessed
- 1 – Very much improved
- 2 – Much improved
- 3 – Slightly improved
- 4 – No change
- 5 – Slightly worse
- 6 – Much worse
- 7 – Very much worse

Date completed: _____ time: _____ Initials: _____

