Appendix 5: Subject Satisfaction Survey

Patient Satisfaction Questionnaire – Day -1 Questions

To be completed by the subject on Study Day -1

1. Please circle the number below that represents how satisfied you are *currently* with your ability to manage your orthostatic hypotension (OH) symptoms. Consider both how effectively you can manage your symptoms and any side effects resulting from the products you currently use.

Very

Dissatisfied w/ Current
OH Symptoms Management

Very

Satisfied w/ Current
OH Symptoms Management

1 2 3 4 5 6

Subject initials: _____

Date Completed: _____

Patient Satisfaction Questionnaire – Day 15 and Day 29 Questions

To be completed by the subject on Study Day 15 and Study Day 29

1. Thinking over the *past week*, please circle the number below that best indicates how satisfied you have been with the ability of the medication you are taking in this clinical trial to manage your orthostatic hypotension (OH) symptoms:

Very

Dissatisfied with
Trial Medication

Very

Satisfied with
Trial Medication

1 2 3 4 5 6

2. Thinking over the *past week*, which statement best describes your impression of *how well* the study medication worked? (check one)

- The study medication didn't seem to work for me at all.
- The study medication provided some relief of my orthostatic hypotension (OH), but not as much as I would like.
- The study medication worked very well.

3. Thinking over the *past week*, which statement best describes your impression of the *side effects* that you experienced from the study medication? (check one)

- I experienced no/minimal side effects.
- I experienced some side effects, but they were acceptable given the efficacy of the study medication.
- I experienced significant side effects.

4. Thinking about your responses to questions 2 and 3 above; please circle the number that represents how likely would you be to continue taking this medication if you were not currently enrolled in a clinical trial?

Very
Likely to **Discontinue**

Very
Likely to **Continue**

1 2 3 4 5 6

Subject initials: _____

Date Completed: _____

Patient Satisfaction Questionnaire – End of Therapy Visit Questions

To be completed by the subject at the end of study therapy (Study Day 140 or at the time of early discontinue, as applicable)

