6.2 Baseline Definition

For the OHQ (OHSA and OHDAS) scores and Clinician's/Subject's Global Impression, baseline is defined as the pre-lunch measurement on Day -1. For the blood pressure, heart rate, and duration of standing, baseline is defined as the pre-breakfast measurement on Day 1. For laboratory abnormalities and ECGs, baseline is defined as the measurement on Day -1.

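### The pressor stop before Part C can be shorter than the one-week recall of baseline OHSA question 1, so up to about 82–83% of a daily pressor user's baseline week may be on pressor, and the SAP has no flag for it

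*Protocol*

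**What the plan says.** Exclusion 4 (Protocol synopsis and section 4.2) has vasoconstricting agents used to raise blood pressure stop "at least 2 days or five half-lives (whichever is longer) prior to dosing on Day 1 of Part A and C", and keeps them out for the whole of Part C. Fludrocortisone is handled separately and is permitted in the washout and in Part C under stated conditions.

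The Part C OHSA (Protocol Appendix 2) asks "how severe your symptoms from low blood pressure have been on the average over the past week". For the OHQ scores, SAP 6.2 states that "baseline is defined as the pre-lunch measurement on Day -1". For blood pressure and standing time the same section uses the pre-breakfast reading on Day 1.

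On timing, the Table 2 footnotes say the questionnaires "should be completed at least 4 hours after dosing (but no more than 7 hours) and before lunch", and that Day -1 "assessments should be prospectively calculated, based on the target Day 1 dosing time".

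SAP 8.2 and 9.2.1 define a responder by a fall of at least 2 units in question 1 at Week 4. SAP 7.3 uses the same baseline score, cut at 4, for the Symptomatic subgroup. No subgroup in SAP 7.3 uses pressor exposure before baseline.

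**The concern.** The recall period is seven days, but the required pressor-free period can be as short as two. A subject who used midodrine or a similar agent between Parts A and C could rate a baseline week spent mostly on that agent. At Week 4 the same subject rates a week on TD-9855 with pressors barred. The question 1 change then compares TD-9855 largely with the earlier pressor. The blood pressure change, whose baseline falls at the end of the stop period, compares TD-9855 with no pressor.

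The primary endpoint, the responder proportion and the Symptomatic class all rest on this baseline score. Protocol section 3.2 also wants to relate blood pressure to symptom relief, which is harder when the two baselines describe different treatment states. The OHDAS items have the same one-week recall, so the secondary composites are exposed too.

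**Working it through.** The documents give no on-pressor share, so there is no planned figure to reproduce. The check is time arithmetic.

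**Inputs**
- Stop time before Part C Day 1 dosing: S = max(48 h, 5 × half-life), from exclusion 4. This is a minimum.
- Recall period: 7 × 24 = 168 h (Appendix 2).
- Questionnaire time: q = 4 to 7 h after the dosing clock time (Table 2 footnotes). Day -1 is the day before Day 1, so the questionnaire falls 24 − q = 20 to 17 h before dosing.
- Assumptions: daily pressor use up to the stop, and even averaging of the week by the subject. Half-lives are not in the documents and are varied below.

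**Share of the recall week on pressor**

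Off-pressor hours = S − (24 − q). On-pressor share = (168 − off-pressor hours) / 168.

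With S = 48 h:
- q = 4: off 48 − 20 = 28 h; share 140/168 = 83.3%
- q = 4.5 (the Protocol's illustrative 8:00 dose and 12:30 questionnaire): off 28.5 h; share 139.5/168 = 83.0%
- q = 7: off 48 − 17 = 31 h; share 137/168 = 81.5%

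This is the most the rule allows. The half-life limb governs once 5 × half-life exceeds 48 h, that is, above 9.6 h.

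| Stop before dosing | How it arises | On-pressor share |
|---|---|---|
| 48 h | half-life up to 9.6 h, stop at the limit | 81.5–83.3% |
| 60 h | assumed half-life 12 h | 74–76% |
| 72 h | earlier stop | 67–69% |
| 120 h | earlier stop, or assumed half-life 24 h | 39–40% |
| 180 h | assumed half-life 36 h | 3–5% |

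The recall week opens 168 + 17 = 185 h to 168 + 20 = 188 h before dosing. The half-life limb alone clears it only at a half-life of 185/5 = 37.0 h to 188/5 = 37.6 h or more.

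**The other assessments**
- Week 4: the SAP 6.3 window for Day 29 is Days 26 to 32. Seven days back from Day 26 is Day 19, so the recall week lies wholly in Part C, where pressors are barred.
- Blood pressure: in the Protocol's illustrative sequence the pre-dose reading is at 7:30 for an 8:00 dose, so 47.5 h after a last pressor dose taken at the 48-hour limit.

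**Size in units of question 1 (assumed pressor effect b)**

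Per-user baseline shift = b × share, with share 0.815 to 0.833:
- b = 0.5: about 0.4
- b = 1: about 0.8
- b = 2: 1.63 to 1.67
- b = 3: 2.4 to 2.5

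To register the 2-unit fall, such a user needs an improvement over the off-pressor level of about 2 + 0.8 = 2.8 units if b = 1, or 3.6 to 3.7 units if b = 2. The shift in the group mean is the proportion of users times the per-user shift. That proportion is unknown and may be zero.

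**The case against.** The strongest objection is that pressor use in the baseline week is implied, not stated. The washout text names only fludrocortisone for managing symptoms. Protocol section 6.3.2 is largely redacted and section 6.3.20 is unreadable, so a rule may sit there. This stands as a limit on size and confidence. Against it, a separate stop before Part C Day 1 has a purpose only if these agents may be resumed after Part A, and exclusion 6 exempts them from the two-week stable-medication rule.

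The SAP also already tabulates prior medications, lists them with concomitant medications, and allows further subgroups with at least 5 subjects. The split is therefore possible, but it is not prespecified.

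A reader might infer more than the documents support:
- **That every pressor user's baseline is 82% on pressor.** That is a ceiling for daily use stopped at 48 h.
- **That Appendix 4 contradicts exclusion 4.** It refers to Day -1 as the visit "when you rated the severity of your orthostatic hypotension after being off medication", but its severity item concerns the moment of rating. A user is then 28 to 31 h off pressor, which agrees with the stop rule.
- **That the Day -1 survey shows pressor use.** Its phrase "any side effects resulting from the products you currently use" is satisfied by permitted fludrocortisone.
- **That TD-9855 from Part A carries over into the baseline week.** How close the last Part A dose can be depends on whether the 8-day minimum washout includes Days -2 and -1, which the text does not settle.

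**Conclusion.** The mismatch between the stop window and the recall period is in the text. For a daily user who stops at the 48-hour limit, up to about 82–83% of the baseline recall week is on pressor, while the Week 4 week must be free of it. If the pressor relieved symptoms and the subject averages the week evenly, three things are biased downward for such users relative to an off-pressor baseline: question 1 improvement, the responder rate, and classification as Symptomatic. Their symptom and blood pressure changes also start from different treatment states. The 0.8 to 1.7 unit shift for b of 1 to 2 rests wholly on that assumed effect.

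It does not follow that Part C as a whole understates the effect of TD-9855. Part C is open-label, uncontrolled and descriptive, and other biases may run the other way. Nor is a subject without recent vasoconstrictors untreated, since fludrocortisone is permitted. This is a cheap improvement to make: it affects what the pooled change can be said to show and does not invalidate the endpoint.

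**What to change.** In SAP 6.2, 7.3 and 9.2.1:

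1. Prespecify a flag, from the prior and concomitant medication records, for any exclusion 4 vasoconstrictor (ephedrine, dihydroergotamine, midodrine or similar) taken in the 7 days before the Day -1 OHQ. Do not count fludrocortisone in the flag; report it separately. The definition must say so, because exclusion 6 lists fludrocortisone among vasoconstricting agents.
2. Report the number flagged. Report Week 4 question 1 change and responder proportion with and without the flag.
3. Describe only the unflagged group as change from a baseline free of vasoconstrictors, and do not call that baseline untreated.
4. Mark subjects whose flag depends on a stop date handled by the SAP 6.4 rules. A missing stop day becomes the last day of the month and a fully missing stop date counts as ongoing, so either can change the flag.

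Separately, the clinical team should reconcile the exclusion 4 stop window with the seven-day recall in Appendix 2. No stop rule is proposed here.

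The cost is one derived variable from data already collected and one split of existing tables. The downside is small groups, so the split supports description only. If nobody is flagged, one line in the report closes the point.
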